## **Purpose of the Study and Background**

### **Background**

Organizational skill impairment occurs in many neurodevelopmental conditions, including attention-deficit/hyperactivity disorder (ADHD) and contributes to school failure, a pernicious mediator of poor long-term outcomes. Impairments in organizational skills have not been addressed by standard behavioral interventions, nor are standard medications for ADHD sufficiently effective for this specific functional domain.

Organizational skills training (OST) was developed in response to the underperformance of stimulant medication to remediate organizational deficits and specifically to target the four impaired domains which worsen school performance, i.e., Tracking Assignments, Managing Materials, Time Management and Task Planning. OST comprises in-person sessions with a therapist, during which previously learned skills are reviewed, new skills are taught and practiced, and instructions are given on when to use the new skill between sessions. Evidence from a two-site randomized controlled trial that OST can produce behavioral improvements in Children's Organizational Skills Scales (COSS) as rated by teachers, with large effect sizes which were maintained for up to 1 year suggests that enduring changes in brain connectivity and intrinsic brain properties likely occurred.

### **Purpose of the Study**

We propose to identify functional changes in large-scale neural systems subserving response to intervention in elementary school-age children impaired in organizational skills. Specifically, we intend to use resting-state functional magnetic resonance imaging (R-fMRI) to capture the physiologic mechanisms underlying behavioral improvements following OST, i.e., the intrinsic functional connectivity (iFC) between dorsal anterior cingulate cortex (dACC) and anterior ventral striatum (aVS).

### **Study Design**

This study includes two phases. The first phase (R61) was an open trial, single arm study, lasting 2 years, with completion of recruitment and data collection in July 2019. The second phase is a randomized two-arm (R33 phase) involving 1:1 randomization to waitlist (WL) control or to OST. In the R61 phase, we screened children (elementary school grades 3-5) to identify participants with organizational skill difficulties to undergo two magnetic resonance imaging (MRI) sessions: one within 2 weeks prior to OST treatment and one within 2 weeks of completion of the OST treatment.

The current randomized two-arm R33 phase will again involve the same treatment (OST) and pre- and post-treatment brain MRI scan. However, 50% of participants will be randomly assigned to receive OST within 2 weeks of successful completion of their first MRI scan (i.e., No-Wait study arm), while the other 50% will

be randomly assigned to receive OST after 12 weeks of waiting (i.e., Waitlist study arm).

## Characteristics of the Research Population

### Number of Subjects

In the R61 phase, we obtained complete datasets (i.e., high-quality pre- and post-OST scans and complete phenotypic data) from at least 22 participants. To reach this number, we enrolled over 50 children for in-person clinical/behavioral assessments, and scanning at least 30 eligible participants.

In the R33 phase, we anticipate screening 144 children to yield 86 with complete data from two sets of MRI scans, obtained after the same interval.

Only children are subjects in this study; parents (and if the child's teacher agrees, teachers) are informants who report on child's behavioral measures and are therefore not study subjects.

### Gender of Subjects

We will recruit both males and females. Despite the marked male preponderance in neurodevelopmental disorders, we will endeavor to recruit at least 30% females.

### Age of Subjects

This is a study of elementary school children in grades 3 – 5, who have one main teacher for at least three of the 4 core academic subjects (English Language & Arts; Math; History/Social Science; Science). The OST intervention is specifically designed for children in elementary school who have a single teacher. Children in the corresponding age ranges (typically 8-12) have been successfully scanned without adverse effects at the NYU Langone Medical Center and at numerous other research facilities.

### Racial and Ethnic Origin

All races and ethnic origins are eligible. Based on prior studies, we expect approximately 25% of participants to self-identify as Hispanic/Latino, and racial composition of participants to be approximately 62% Caucasian, 24% African American, 4% Asian, 1% American Indian, and 9% Other.

### Inclusion Criteria

- Student in grades 3-5 of elementary school having one main teacher corresponding to ages between 8 and 12 years-of-age
- Children may be designated as obtaining special education assistance as indicated on an Individualized Education Program (IEP), provided a review of the current IEP by the research team under the supervision of the PI indicates that the child has a broadly average reading level and language development.

- Written assent by child and consent by parent or legal guardian
- IQ: Estimated full scale IQ  $\geq 85$  and language comprehension standard scores  $\geq 8$  is required as in past studies to assure that children are able to comply with specific skills training and to minimize neurobiological heterogeneity
- Organizational skills deficits defined as elevated ( $\geq 1SD$ ) pre-treatment COSS Parent Total T-score and at least one COSS Parent Interference item rated as either a 3 or 4 (indicating an above-average level of impairment)
- Handedness: given the greater prevalence of non-right-handedness in neurodevelopmental disorders, we will track handedness but not exclude left-handed individuals
- Medication: To minimize variability due to medication effects, we will preferentially recruit currently unmedicated individuals (no psychotropic medications in the previous month). For allowed medications, we will require that dosage be stable for  $>2$  weeks before study entry
- Must provide adequate MRI data at baseline

### **Exclusion Criteria**

- Enrolled in a self-contained special education classroom or served by a 1:1 paraprofessional in their classroom
- Absence of signed consent by parent or legal guardian
- Children who dissent regardless of parental permission
- Full scale IQ  $< 85$
- Children with a recent (past 6 months) or current history of neuroleptic treatment or current treatment with psychotropic medications other than stimulants, or guanfacine or atomoxetine
- Per history (and medical records if needed) medical illness requiring chronic current treatment
- History of intrathecal chemotherapy or focal cranial irradiation
- Premature birth ( $< 32$  weeks estimated gestational age or birth weight  $< 1500g$ )
- History of leukomalacia or static encephalopathy, intracerebral hemorrhage beyond grade 2, other specific or focal neurological or metabolic disorder including epilepsy (except for resolved febrile seizures)
- History of traumatic brain injury
- Contraindication for MRI scanning (metal implants, pacemakers, metal foreign bodies or pregnancy)

### **Vulnerable Subjects**

This study does not involve greater than minimal risk. It enrolls children in 3rd-5th grade (typically between ages 8 and 12). In compliance with IRB standards for research with vulnerable populations, a description of risks and benefits is included in the Risk/Benefit Assessment section. We will not enroll emancipated minors or mature minors and will therefore require written consent by a parent or legal guardian

as well as child assent, in accordance with IRB regulation. We describe the procedure for obtaining consent and assent in the relevant section below.

## Methods & Procedures

### Methods & Procedures

This study involves the following steps:

1. Pre-screening. Interested parents/legal guardians will speak with study staff over the phone for the purpose of screening (“*Telephone\_screening\_form.doc*”) to determine basic inclusionary and exclusionary information. If the parent/legal guardian endorses any exclusionary criteria or fails to endorse inclusionary criteria over the phone, then the study staff will inform them that the study would not be appropriate. If the parent/legal guardian does not endorse any exclusionary criteria and endorses all inclusionary criteria, then the study staff will make the parent COSS forms available to the parent (via mail or if preferred, via secure web-based platforms, e.g., REDCap <https://openredcap.nyumc.org/apps/redcap/>). If inclusionary criteria are met based on these forms (detailed in the Inclusionary Criteria section), then the screening visit will be booked during which full consent and assent will take place. Only children are subjects; parents (and, if the child’s teacher agrees, teachers) are informants on child’s behavior, and thus are not study subjects.
2. In-person evaluation visit. The last set of exclusionary and inclusionary information (with the exception of having an MRI scan that provides data meeting our quality criteria) will be gathered at the screening visit. The section **Cognitive Behavioral Measures** details all the assessments to take place during this visit. During the evaluation visit, children will also practice in the MRI simulator (detailed in section **MRI session** below).
3. First MRI visit pre-OST treatment (detailed in section **MRI session** below).
4. If after the MRI visit the child has met all criteria (i.e., data quality on the MRI scan acquired is good), then the child will be assigned to either the No-Wait study arm (i.e., to begin receiving the OST intervention, optimally within 2 weeks of the successful MRI scan) or to the 12-week wait period (Waitlist study arm) at the end of which the subject completes their second MRI scan, and then proceeds to receive OST.
5. OST intervention (detailed in section **OST intervention** below).
6. Second MRI visit: for the treatment arm, this scan is post-OST treatment, optimally within 2 weeks of OST completion (detailed in section **MRI session** below). For the waitlist control condition, this scan is ~12 weeks after their first scan and before proceeding to OST.

#### **Cognitive behavioral measures (identical for both the R61 and R33 phases)**

Cognitive capacity for study eligibility will be verified based on full scale IQ  $\geq 85$  estimated from the two-subtest *Wechsler Abbreviated Scale of Intelligence-2nd ed.*

(WASI-II) (or where indicated, the equivalent *Wechsler Intelligence Scale for Children-Fifth Edition* (WISC-V)) and scores  $\geq 8$  on *Understanding Spoken Paragraphs, Formulated Sentences* scales and for children aged 9.0 and above, the Multiple Meanings Metalinguistic module of the *Clinical Evaluation of Language Fundamentals-5th ed* (CELF). For visits taking place during the COVID-19 pandemic, to further support social distancing, the cognitive behavioral measures described above will be administered using the digital Pearson's Q-global platform which has been vetted by NYU Langone's MCIT. As supported by Pearson's Technical Reports "Equivalence of Q-interactive™ and Paper Administrations of Cognitive Tasks: WISC®-V" and the "Using the WASI®-II with the WISC®-V", estimating IQ using either the paper or the digital version of either test is equivalent for children in the 9-12 years old range.

Parents (COSS-P) (and teachers, if the child's teacher agrees to be an informant (COSS-T)) will serve as informants (only the child is a study subject) who will provide baseline and outcome ratings. Furthermore, the Homework Problem Checklist (HPCL) and Academic Progress Report (APR) will be collected to assess generalization of OST benefits to progress in school performance.

Additional phenotypic characterization will be obtained to confirm inclusion criteria and enable dimensional brain-behavior analyses using the following widely used instruments.

Psychiatric disorders will be established by clinicians administering the new computerized DSM-5 KSADS-COMP, based on the KSADS-PL, to parents; all symptoms are measured dimensionally on a 4-point scale and scores and notes entered on a computer.

The parent (and, if the teacher agrees to be an informant, the teacher) *Strengths and Weaknesses of ADHD Symptoms and Normal Behavior* (SWAN) provide dimensional measures of inattention, hyperactivity and oppositionality.

The *Wechsler Individual Achievement Test-3rd ed.* (WIAT-III) is an abbreviated assessment of spelling, mathematics and reading achievement. The *Vineland Adaptive Behavior Scales, Third Edition* (Vineland-3) is a parent interview of adaptive skills.

Besides interviews, parents will complete questionnaires. The *Social Responsiveness Scale-2* (SRS-2) is a widely used dimensional index of autism spectrum disorder (ASD). To assess psychopathology using empirically validated instruments in widespread use, we will include the parent *Child Behavior Checklist* (CBCL).

The *Family Environment Scale* (FES) will be obtained to quantify family conflict. *Hollingshead Index of Social Status* (for comparability with other studies), family

income, birth-date, sex, race, and ethnicity will also be collected as part of the demographic questionnaires.

Pre- and post-intervention administrations of the Cogstate Brief Battery <https://cogstate.com/featured-batteries/cogstate-brief-battery/> will also be adopted.

In response to encouragement from funding agency program staff, the Clinical Global Impressions scale will be included before and after completion of OST.

The Biber Cognitive Estimation Test (questions uploaded on research navigator) will more directly capture potential difficulties in estimating time and quantities.

### **OST intervention**

We will deliver OST targeting three core organizational skills domains – Tracking Assignments, Managing Materials and Time Management – in a program consisting of sessions over 12 weeks, each training lasting about 1 hour, and corresponding 30-60 minute weekly review sessions with the parent and the child, 2-3 days following each training session. Sessions will take place remotely by an encrypted video call (i.e., via WebEx secure, encrypted online link accessible on mobile, desktop and tablet devices [https://cisco-support.webex.com/guest/articles/en\\_US/Usability\\_FAQs/WBX70618/](https://cisco-support.webex.com/guest/articles/en_US/Usability_FAQs/WBX70618/)). The review sessions will allow more timely feedback by the therapist regarding content or implementation questions that may have arisen after the training session. If the child and parent report no difficulties practicing the new skill, the therapist will reinforce continued reporting of child's progress.

As typical in the field, to ensure the fidelity of OST treatment implementation, before commencing the study we will first train therapists to deliver the OST program. Training cases will not undergo the MRI scanning, which decreases time-commitment burden to the families. Furthermore, children with contraindications for MRI scanning (metal in the body, such as braces) would be therefore eligible to receive the OST program. Notably, the potential benefit of this study is in the OST intervention; therefore training cases still receive the maximum potential benefit as the study participants who receive the MRI and the OST.

### **MRI session**

Within a week prior to the MRI session, children will be familiarized with the scanner environment by playing a computer game while lying down in a colorfully decorated MRI scanner simulator at the Child Study Center. A *Social Story* will be read aloud to prepare the child for the scanning experience. Our team has a long track-record of obtaining high-quality imaging data in neurodevelopmental disorders, including ADHD and autism, with children as young as 5 years old.

Imaging will be performed using a research-dedicated 3T Siemens Prisma MRI scanner with a 32-channel Siemens head/neck coil, both of which have been FDA-approved for clinical and research scans as minimal risk devices. No exogenous

contrast agent will be used in any imaging sequence. At the beginning of the scan session, participants will be familiarized with the scanning environment and the research team, while the imaging procedures are being carefully explained. The *Social Story* will be read aloud again. The research staff will conduct a metal screening interview with the parent(s) to ensure MRI safety, and will use a hand-held metal detector to search for any metal on the participant (and the parent if they plan on entering the scanner suite while the child is being set-up). Additionally, female participants who have begun menstruation (extremely rare occurrence in our targeted age range) will be instructed to take a urine pregnancy test to ensure lack of pregnancy. If there are no contraindications, participants will be brought into the MRI room. The research staff will place earplugs, headphones, pneumatic belt, and finger transducer (see below) on the child and have him or her lay down on the scanner table. The participant will be positioned on their back on the scanner gantry with head straight aligned with the middle of the coil. The radio frequency imaging coil, which obtains the imaging data, will be positioned in front of the child's face. All participants will be asked to limit head motion. Foam padding will be used for comfort and to comfortably restrict head motion. Once the child is comfortable, we will slide the scanner table into the magnet and begin scanning. Between each scan, the child will be in contact with the research staff through a microphone mounted in the MRI scanner. While scanning is on it gets loud, thus the speaker is turned off and we will not be able to hear the child. This is why the child will have a handheld squeeze-ball device to let the operator know if s/he wishes to immediately stop scanning and be removed from the magnet. The MRI scan can be stopped at any time at her/his request; when s/he squeezes the squeeze-ball, it emits a loud sound in the operator room to notify the research staff who will immediately stop the scan. We spend time during the mock MRI to instruct and coach the child of these procedures so s/he will be prepared before the MRI scan.

## **Data Analysis and Data Monitoring**

### **Data Analysis**

Our primary scientific target is iFC between dorsal anterior cingulate cortex (dACC) and anterior ventral striatum (aVS). Specifically, we will calculate the effect size of the decrease from pre- to post-treatment in dACC-aVS iFC, and will assess the amount of variance in improvement in parent COSS total T-scores that is explained by the change in iFC between dACC and aVSFP (i.e., within the subset of voxels in aVS mask corresponding to the FP subregion: <https://osf.io/5m5sx/>).

Analyses testing H1 will utilize the data from all subjects (comprising the samples derived from the Bayesian dynamic borrowing) in a linear model for  $dACC\text{-}aVS$  iFC as a function of treatment (OST vs. WL) and controlling for baseline iFC, age and sex. A significant regression coefficient for treatment would indicate that the post-treatment iFC measure differs between those who received OST and those on WL. Detectable effects: with estimated sample size of 65 for OST, there is 80% power at  $\alpha=0.05$  (2-tailed) to detect a difference between OST and WL of magnitude Cohen's  $d=0.56$ . With an estimated sample size of 43 for OST, the detectable effect is  $d=0.61$ . Such a medium to large effect size is considered clinically significant.

**Aim 2 H2, H3a, H3b** ( *$dACC\text{-}aVS_{FP}$  iFC changes will mediate changes in clinical and academic measures*).

The Sobel mediation test in SPSS will be employed to evaluate these relationships. With 86 children power =80% at  $\alpha=0.05_{(2-t)}$  to detect  $r=0.3$ , between change in iFC and change in COSS,  $\sim 10\%$  explained variance. Power =80% at  $\alpha=0.05$  to detect a  $d=0.61$  effect with  $n_{OST}=43$  (or  $d=0.56$ , if effective  $n_{OST}=65$ ).

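### Aim 2 is worded in change scores with no baseline terms named; read that way, the randomised OST-to-iFC path of the mediation test is less precise than the H1 form would make it

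*Combined protocol and SAP*

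**What the plan says.** In the Statistical Plan (R33 phase), Aim 1 H1 is a linear model for dACC-aVS iFC on treatment, "controlling for baseline iFC, age and sex". The treatment coefficient is therefore a baseline-adjusted effect.

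Aim 2 (H2, H3a, H3b) is worded differently. Its hypothesis is that dACC-aVS_FP "iFC changes will mediate changes in clinical and academic measures". The only analysis named is the Sobel mediation test in SPSS. The power sentence uses a correlation of 0.3 "between change in iFC and change in COSS" in 86 children, then repeats the H1 detectable effects of d = 0.61 and d = 0.56. The Data Analysis section also relates change in iFC to improvement in the parent COSS score.

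No equation is given for either mediation path, and baseline covariates are neither included nor excluded.

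**The concern.** A mediation test of this kind rests on two regressions: iFC on arm (path a) and outcome on iFC and arm (path b). If path a is fitted to the simple difference between scans, the slope on baseline iFC is fixed at 1. Unless the retest correlation is perfect, that leaves more residual variance than estimating the slope. Below rho = 0.5, a change score is noisier than ignoring baseline altogether.

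Aim 2 is the trial's mechanistic question, and the Sobel statistic needs both paths to be well estimated. The plan already uses the efficient form for H1. Leaving it out of Aim 2 would give away precision on the one mediation path that randomisation protects.

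**Working it through.** **Inputs from the documents.** Two-sided alpha of 0.05 and 80% power (Statistical Plan); "involving 1:1 randomization to waitlist (WL) control or to OST" (Study Design); "86 with complete data from two sets of MRI scans" (Number of Subjects), hence 43 per arm. Detectable effects: d = 0.61 at 43 v 43 and d = 0.56 at 65 v 43. Correlation: r = 0.3, n = 86.

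**Assumptions.** Retest correlation rho from 0.3 to 0.7, equal SDs at the two scans, and 0.61 read in time-2 SD units. The documents state none of these.

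**Step 1: the plan's own figures.**
- 43 v 43: noncentrality 0.61/sqrt(2/43) = 2.83, 84 df, power 79.8%.
- 65 v 43: 0.56/sqrt(1/65 + 1/43) = 2.85, power 80.6%.
- Correlation (Fisher z): atanh(0.3) × sqrt(83) − 1.96 = 0.86, power 80.5%.

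All three reproduce. The last is a plain two-variable correlation with no covariates.

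**Step 2: variance on path a.** With unit variance at each scan, the change score has variance 2(1 − rho) within arm and the baseline-adjusted residual has 1 − rho². The ratio is 2(1 − rho)/[(1 − rho)(1 + rho)] = 2/(1 + rho).

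**Step 3: power on path a.** The standardised effect is 0.61/sqrt(2(1 − rho)) for change and 0.61/sqrt(1 − rho²) for adjusted. Power uses the noncentral t with 84 df; the few df spent on covariates are ignored.

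| rho | Variance, change | Variance, adjusted | Ratio | Effect, change | Effect, adjusted | Power, change | Power, adjusted |
|---|---|---|---|---|---|---|---|
| 0.3 | 1.40 | 0.91 | 1.54 | 0.516 | 0.639 | 65.7% | 83.4% |
| 0.5 | 1.00 | 0.75 | 1.33 | 0.610 | 0.704 | 79.8% | 89.8% |
| 0.7 | 0.60 | 0.51 | 1.18 | 0.788 | 0.854 | 95.0% | 97.5% |

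**Step 4: check by simulation** (86 children, 43 per arm, true path a 0.61, 2,000 trials per setting). Mean path a was 0.59 to 0.62 in both forms. The SE was 0.254 (change) v 0.206 (adjusted) at rho 0.3, and 0.167 v 0.155 at rho 0.7. The squared ratios, 1.52 and 1.16, agree with the formula.

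**Step 5: effect on the Sobel test.** Adding baseline iFC to path a alone, with path b left on change scores, raised Sobel power in every setting simulated, for example from 39% to 56% and from 58% to 61%. A repeat with 4,000 trials, path b 0.3, direct effect 0.3 and COSS following iFC change gave 41% to 50% with both retest correlations at 0.5, and 58% to 63% with both at 0.7.

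**Step 6: path b behaves differently.** Differencing also widens the spread of the predictor. The SE ratio, change to adjusted, is about sqrt((1 + rho_iFC)/(1 + rho_COSS)). It is 1.00 when the two are equal, 0.87 at 0.3/0.7 and 1.14 at 0.7/0.3. Bias depends on how iFC and COSS are linked:
- If COSS follows post-baseline iFC with a true slope of 0.30, the change-score slope is attenuated to 0.19 to 0.26.
- If COSS follows the iFC change itself, the change-score slope is unbiased.
- If baseline iFC and COSS correlate 0.3 (assumed), that link decays over time and nothing later connects them, path b alone rejects 6 to 13% of the time on change scores. The Sobel test rejects 2 to 3%.
- If they share stable traits measured with error, the baseline-adjusted path b rejects 7 to 27% (Sobel up to 11%), against about 5% on change scores.

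**The case against.** The strongest reply is that the plan never says Aim 2 is unadjusted. The change wording comes from a hypothesis and a power sentence, and adding baseline to a change-score model gives the same arm coefficient as modelling time-2 iFC. The wording is therefore compatible with adjustment. This stands: the unadjusted reading is an inference from silence, though the natural one given that H1 lists its covariates and Aim 2 lists none. If adjustment was intended, the plan still has to say so, and the remedy is the same.

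A reader might go further in three ways that the documents do not support:
- *Both paths lose precision.* Path b does not in general. Its SE is equal or smaller on change scores unless iFC is more stable than COSS.
- *The OST effect in Aim 2 differs from that in H1 because of change scores.* Under 1:1 randomisation both forms target the same mean effect and differ only in precision. What does separate the two analyses is the region: dACC-aVS in H1, dACC-aVS_FP in Aim 2. Borrowed single-arm R61 children could also make the two forms diverge if they differ at baseline.
- *Change scores inflate the false-positive rate of the mediation test.* The inflation found was on path b alone, under one assumed baseline structure. The Sobel test stayed below 5% there, and under another structure adjustment is the form that misleads.

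**Conclusion.** The point holds for the randomised path only. As Aim 2 is written, the OST-to-iFC estimate carries 54%, 33% or 18% more variance than necessary at rho 0.3, 0.5 or 0.7. The loss is about 18, 10 and 2.5 percentage points of power at 0.61 time-2 SD.

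The variance ratio needs only equal SDs at the two scans. The power figures also need the assumed rho and the reading of 0.61 as time-2 SD units, so the size of the loss cannot be fixed from the documents. If rho is 0.7 or higher, the loss is small.

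For the iFC-to-outcome path, the finding is that the model is unspecified. The choice between change scores and baseline adjustment is a trade-off between assumptions that the trial cannot verify.

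**What to change.** 1. **Path a.** In Aim 2, regress time-2 dACC-aVS_FP iFC (or its change) on arm, baseline dACC-aVS_FP iFC, age and sex. The arm coefficient is the same either way, so results can still be described as change.
2. **Path b.** Write out the regression, name one primary form, and report the other as a sensitivity analysis: change on change with arm, and the same model with baseline iFC and baseline outcome added.
3. **Region.** State that the Aim 2 mediator is the FP subregion, so that its OST effect is not read as a repeat of H1.
4. **HPCL and APR.** Confirm that both are collected at baseline before naming them as covariates. The cognitive behavioral measures section states baseline and outcome ratings for COSS but gives no timing for these two.

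The cost is SAP wording and, on path a, three degrees of freedom out of 84. The first scan is acquired before assignment, and birth date and sex are already collected, so path a needs no new data. The sensitivity analysis on path b adds one model per outcome.

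### Aim 2 names a Sobel test, but its power basis and the planned explained-variance figure carry no arm term; if computed over both arms, OST effects on each measure would inflate the iFC-COSS association

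*Combined protocol and SAP*

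**What the plan says.** The Aim 2 hypothesis in the Statistical Plan is one of mediation: "iFC changes will mediate changes in clinical and academic measures". The Sobel mediation test in SPSS "will be employed to evaluate these relationships". The plan does not write out the exposure, the path equations or the covariates. Treatment and covariates are written into a model only for H1 under Aim 1.

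The next sentence gives the power: "With 86 children power =80% at" two-tailed alpha 0.05 to detect r=0.3 "between change in iFC and change in COSS", glossed as roughly 10% explained variance. The 86 are both R33 arms. Number of Subjects says "we anticipate screening 144 children to yield 86 with complete data from two sets of MRI scans", allocation is 1:1, and the Statistical Plan expects at least 43 per group.

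The Data Analysis section adds that the investigators "will assess the amount of variance in improvement in parent COSS total T-scores that is explained by the change in iFC" between dACC and the FP subset of aVS voxels. It mentions no arm and does not name the sample.

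The same explained-variance quantity, at a threshold of 10%, was a milestone in the single-arm R61 phase.

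**The concern.** In R61 every child received OST, so a correlation between iFC change and COSS change was an association among treated children. In R33 half the children are on the waitlist at the second scan. Treatment arm is then a common cause of both changes. If OST lowers iFC and also lowers COSS by another route, the two changes correlate across the pooled sample although neither predicts the other within an arm.

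A separate route is plausible here. COSS is rated by parents, who know the arm and take part in the weekly OST review sessions.

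The mechanistic claim is at stake. A pooled explained variance would grow with OST's effectiveness on the two measures and could be read as iFC explaining improvement.

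**Working it through.** **1. The plan's own figures.** For one Pearson correlation, power = Φ(atanh(r)·√(n−3) − 1.96). With r=0.3 and n=86: 0.3095 × 9.110 = 2.820, and Φ(0.860) = 80.5%. The n needed for 80% is 85. The stated 80% therefore reproduces as a single correlation over all 86 children. A two-sample t-test with 43 per arm gives a detectable d of 0.611, which matches the plan's 0.61.

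**2. Inputs for the check.**
- OST effect on iFC: d_M=0.61, the plan's detectable effect with 43 per arm; 0.4 as a lower case.
- OST effect on parent COSS: no figure is given. The Background reports an earlier trial "with large effect sizes which were maintained for up to 1 year", but for teacher ratings. I assume d_Y of 0.8 to 1.2.
- Within-arm correlation of the two changes: zero, the case of no link.

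**3. Correlation created by arm alone.** With 1:1 allocation and unit within-arm variance, arm adds d²/4 to each variance and d_M·d_Y/4 to the covariance:

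r = (d_M·d_Y/4) / √[(1+d_M²/4)(1+d_Y²/4)]

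Rejection is for a nominal 5% test of r=0 with n=86, by the formula in step 1 with both tails.

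| d_M | d_Y | r | r² | Rejects |
|---|---|---|---|---|
| 0.61 | 0.8 | 0.122/1.126 = 0.108 | 1.2% | 16.8% |
| 0.61 | 1.0 | 0.1525/1.169 = 0.130 | 1.7% | 22.3% |
| 0.61 | 1.2 | 0.183/1.219 = 0.150 | 2.3% | 28.1% |
| 0.4 | 0.8 to 1.2 | 0.073 to 0.101 | 0.5 to 1.0% | 10 to 15% |

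Simulation with 43 per arm agrees, at about 17 to 29% for d_M=0.61. With arm in the COSS model, the iFC coefficient rejects in 5%.

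**4. The named test under the same no-link assumption.** A Sobel test whose mediator-to-outcome path is adjusted for arm rejects in about 1%. With that path unadjusted, it rejects in about 7 to 15%.

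**5. Power once arm is included.** For partial r=0.3 given arm, √(n−4) replaces √(n−3): 0.3095 × 9.055 = 2.803, and Φ(0.843) = 80.0%.

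**6. Power of the Sobel test itself.** Take d_M=0.61 and within-arm r=0.3.
- The OST-to-iFC path has expected z of about 0.61/√(2/43) = 2.83.
- The iFC-to-COSS path has expected z of about (0.3/√0.91)·√83 = 2.86.
- The Sobel statistic is then about 2.83 × 2.86/√(2.83² + 2.86²) = 2.01, barely above 1.96.
- Simulated power is about 42 to 44%.

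**The case against.** The strongest reply is that the correlation sits in a power sentence and is not the planned analysis. The test is Sobel, randomised arm is its natural exposure, and its usual form adjusts the mediator-to-outcome path for exposure. This stands. A reader might infer that Aim 2 is simply a pooled correlation, or that it lacks a valid null; the plan supports neither, and a standard Sobel test is conservative here. What remains open is that the plan never writes the models down, and step 4 shows that the choice matters.

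Second, the Data Analysis sentence may not concern both arms. It speaks of change from before to after treatment and resembles the R61 milestones, while waitlist children have both study scans before OST. This also stands, so the inflation is conditional on computing the figure over both R33 arms. However, the sentence is in the future tense, R61 data collection ended in July 2019, and nothing limits it to treated children.

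Third, a reader might infer that true power for the association is 39 to 51%, not 80%. That follows only if r=0.3 is read as a marginal correlation, leaving a partial r of about 0.18 to 0.22. The plan does not say which is meant, and read as a partial correlation its 80% holds.

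Fourth, the inputs are imperfect. The d of 0.61 is a detectable effect, not an expected one, and under Aim 1 it refers to dACC-aVS iFC, not to the FP subset used as mediator. The COSS effect is assumed. At these inputs arm alone explains 1.2 to 2.3% of variance, well short of 10%, so it inflates a result and does not manufacture the full target.

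**Conclusion.** The point holds in a conditional form. The only iFC-COSS association quantified for R33 covers both arms without an arm term, and so does the explained-variance report as written, since it sets no limit by arm. If that report is computed over both arms, separate OST effects on iFC and COSS raise a nominal 5% error rate to about 17 to 29% at iFC d=0.61, or 10 to 15% at d=0.4. This rests on an assumed parent-COSS effect of 0.8 to 1.2 and no within-arm link. The Sobel test is safe if its second path is adjusted for arm, which the plan leaves unstated.

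Separately, the stated 80% is power for a correlation. It should not be read as power for the indirect effect, which is a little over half as large under the plan's own effect sizes. This is a cheap improvement, not a flaw that invalidates Aim 2.

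**What to change.** In the Aim 2 text and the Data Analysis section:

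- Name randomised arm as the exposure in the Sobel test, and write out both path models with their covariates.
- Include arm in the COSS (mediator-to-outcome) model.
- Report explained variance as the R-squared gain when iFC change is added to a model with arm and covariates. If the figure is meant for treated children only, say so. Power for r=0.3 would then be about 50% with 43 children and 68% with an effective 65.
- Word the power line as partial r=0.3 given arm (80.0% with 86 children), and note that power for the indirect effect is about 42 to 44% at iFC d=0.61 and within-arm r=0.3.

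The cost is a few sentences and one degree of freedom. The reported explained variance will probably be smaller.
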